3.4 Relative Bioavailability Analysis Set

The Relative Bioavailability Analysis Set is defined as the subset of subjects in the PK Parameters Analysis Set who have at least one primary PK parameter (AUC_{0-t} , AUC_{0-inf} and C_{max} of sitravatinib) in both periods.

The following are reasons for exclusion from the Relative Bioavailability Analysis Set:

- Subject is not included in the PK Parameters Analysis Set.
- Subject does not have at least one of the primary sitravatinib PK parameters AUC_{0-t} , AUC_{0-inf} or C_{max} for both periods.

The Relative Bioavailability Analysis Set will be used as the analysis set for the bioavailability analysis.

3.5 Analysis of Subgroups

No subgroup analyses are planned for this study.

4. Study Measures

This section describes the measures that were collected and/or derived during the study at the time points specified in the Schedule of Assessments (Section 2.5).

4.1 Safety Measures

The safety endpoints described in this section will be analysed according to the analysis methods described in Section 6.8.

4.1.1 Exposure to Study Drug

Study drug administration information, including the date and time of the administration and the actual dose administered will be reported on the 'Dose Administration' CRF page.

4.1.2 Adverse Events

An adverse event (AE) is defined as any unfavorable and unintended sign including an abnormal laboratory finding, symptom or disease associated with the use of a medical treatment or procedure, regardless of whether it is considered related to the study treatment or procedure, that occurs during the course of the study.

Adverse events data will be collected and recorded on the 'Adverse Event' CRF page from the time that informed consent was given, for the duration of the trial.

Missing and partial AE dates will be handled according to the rules specified in Sections 5.1.4 and 5.6.2.1.

4.1.2.1 Adverse Event Definitions

Treatment emergent adverse events (TEAEs) are defined as AEs that commenced on or after the first study drug administration. If only partial information is available, the rules specified in Section 5.6.2.1 will be applied to determine treatment emergence. TEAEs will be assigned to the last treatment that was administered prior to the start or worsening of the event. If an AE cannot be assigned based on the available information, the AE will be assigned to both treatment groups.

Treatment-related AEs are defined as AEs where the relationship to study drug is reported as 'Related' or is missing. An AE will be classified as not related to study drug if the relationship to study drug was recorded as 'Not Related'.

Serious AEs (SAEs) are defined as AEs where the events are reported as serious.

Sponsor: BeiGene, Ltd.
Protocol Number: BGB-Sitravatinib-101

Severe AEs are defined as AEs where the event severity rating is reported as 'Severe', 'Life-threatening' or 'Death' or missing.

Adverse events leading to the withdrawal of study drug are defined as AEs where the action taken with study drug is reported as 'Dose Withdrawn'.

Adverse events leading to study withdrawal will be defined as AEs where the reason for study withdrawal (on the 'Study Completion' CRF page) was recorded as being an AE.

4.1.2.2 Coding of Adverse Event Terms

Adverse event terms (Investigator terms) will be coded to a lowest level term (LLT), preferred term (PT), high level term (HLT), high level group term (HLGT) and a system organ class (SOC) according to the Medical Dictionary for Regulatory Activities (MedDRA) dictionary, Version 23.0, depending on the latest version available during the study. Although there can be multiple SOCs for a PT, each PT will be linked with one SOC, namely the primary SOC which is automatically assigned by MedDRA via a single HLT, HLGT route.

4.1.3 Laboratory Evaluations

Laboratory evaluations will be performed in accordance with the Schedule of Study Events (Section 2.5). Blood and urine samples will be collected, analysed by a local laboratory and the results will be reported on the CRF.

In the event that the results for a specific laboratory test are not required by the study protocol (for example, only one subject has data for a specific test that was performed in error) or for urine microscopy tests that were only required in the presence of abnormal urinalysis results, the results will not be included in the summary tables, but the data will be listed.

The test panels and parameters presented in the Table 3 will be collected and analysed.

Parameter names will be based on the Clinical Data Interchange Standards Consortium (CDISC) Study Data Tabulation Model (SDTM) Controlled Terminology terms. The mapping of the reported parameter names to the standardised names will be presented in the SDTM specifications. Parameters will be presented in the order specified in Table 3.

In the event that the results for a parameter were reported in different units, the results (including the actual measurement and the normal range limits) will be converted to the Système International (S.I.) unit for the specific parameter and the standardised results/units will be reported. The specific conversion rules will be documented in the SDTM specifications.

If a result for a parameter that is normally considered continuous is reported as a range (i.e., the result for basophils is reported as '<0.01' for a single time point), the result may be converted to a numeric value that is smaller than the reported result to contribute to the derivations and the summary statistics. Any conversion rules that are applied will be highlighted in the footnotes of the affected tables and listings. The original reported result value will however be included in the listing.

If a re-test was performed at any visit, the results from the repeat test will be used in all analyses for the specific visit. The repeat test result will be flagged in the data listing.

Where applicable, parameter names in the outputs will comprise of the test name and the standardised unit of measure (if applicable), for example, 'Albumin (g/L)'. If a specific test is qualitative or unitless, the parameter name will be the test name only.

For all parameters where a normal range limit value was reported, the normal range will be derived based on the available lower and upper limit values and any reported mathematical symbols. If both a lower and upper limit value is available, the normal range will be presented as '(Lower, Upper)'. In the event that only one of the limit values exist, 'N/A' will be used to replace the 'missing' limit value (for example, '(N/A, Upper)'), unless a direction has been specified, in which case the normal range will be displayed as '< or > Limit'.

Table 3 Laboratory Assessments

Clinical chemistry:	Hematology:	Urinalysis:
Alanine aminotransferase Albumin Alkaline phosphatase Aspartate aminotransferase Bilirubin total (fractionate [direct and indirect bilirubin] only if total bilirubin is > upper limit of normal) Blood urea nitrogen Calcium Chloride CO ₂ /bicarbonate Creatinine Gamma-glutamyl transferase Glucose Phosphorus Potassium Sodium Total protein	Hematocrit Hemoglobin Mean cell hemoglobin Mean cell hemoglobin concentration Mean cell volume Platelet count Red blood cell (RBC) count White blood cell (WBC) count WBC differential: Basophils Eosinophils Lymphocytes Monocytes Neutrophils	Bilirubin Blood Glucose Ketones Leukocyte esterase Nitrite pH Protein Specific gravity Urobilinogen Microscopic examination (if protein, leukocyte esterase, nitrite, or blood is positive)
Serology ^a :	Drug screen:	Hormone panel:
Hepatitis B surface antigen Hepatitis C antibody Human immunodeficiency (HIV-1 and HIV-2) antibodies and p24 antigen	Including but not limited to: Amphetamines/methamphetamines Barbiturates Benzodiazepines Cocaine (metabolite) Methadone Phencyclidine Opiates Tetrahydrocannabinol/cannabinoids Cotinine test Alcohol test ^b	Thyroid-stimulating hormone ³
SARS-CoV-2 test ^a :		
COVID-19 Swab Collection & Analysis		

^a Only analyzed at Screening.

^b Only analyzed at Check-in (both dosing periods). Alcohol testing not included at Screening.

Quantitative parameter results will be classified as 'Normal' (within the normal range) or 'Abnormal' (outside the normal range) according to the subjects' individual normal ranges that were provided by the analysing laboratory. Abnormal results will further be classified as being 'Low' or 'High' depending on whether the result is below or above the normal range limits. The clinical significance of any abnormal results will be determined by the Investigator and reported on the CRF.

Qualitative parameter results (excluding serology, SARS-CoV-2 test, urine drug test and alcohol breath test) will be classified as 'Normal' or 'Abnormal' based on the absence (results reported as 'Negative', 'None', 'Null', etc.) or presence (results reported as 'Positive', 'Trace', '+', etc. or where the

Sponsor: BeiGene, Ltd.
Protocol Number: BGB-Sitravatinib-101

result is outside of the normal range) in the findings for the specific parameter. All other test results will be presented as reported.

Baseline and change from baseline values will be derived for each parameter (as appropriate) in accordance with the methods defined in Section 5.1.2.

4.1.4 Electrocardiogram (ECG) Evaluations

Electrocardiogram (ECG) evaluations will be performed in accordance with the Schedule of Study Events (Section 2.5).

The following parameters will be assessed, and measurements and findings will be reported on the 12-Lead ECG CRF page:

- Overall Assessment ('Normal', 'Abnormal Not Clinically Significant [NCS]' or 'Abnormal Clinically Significant [CS]').
- Heart Rate (bpm).
- RR Interval (msec).
- PR Interval (msec).
- QRS Duration (msec).
- QT Interval (msec).
- QTcB Interval (msec).
- QTcF Interval (msec).

Baseline and change from baseline values will be derived for each parameter (as appropriate) in accordance with the methods defined in Section 5.1.2.

Based on the criteria presented in Appendix 1, abnormal ECG measurements ('Low' or 'High') will be identified and reported at each visit and/or scheduled time point.

4.1.5 Vital Signs Evaluations

Vital signs evaluations will be performed in accordance with the Schedule of Study Events (Section 2.5).

The following parameters will be assessed, and measurements and findings will be reported on the Vital Signs CRF page:

- Height (cm).
- Weight (kg).
- Body Mass Index (kg/m²).
- Supine systolic blood pressure (SBP) (mmHg).
- Supine diastolic blood pressure (DBP) (mmHg).
- Supine pulse rate (bpm).
- Respiratory rate (breaths/min)
- Temperature (°C)

Baseline and change from baseline values will be derived for each parameter (as appropriate) in accordance with the methods defined in Section 5.1.2.

Based on the criteria presented in Appendix 2, abnormal vital signs measurements ('Low' or 'High') will be identified at each visit and/or scheduled time point and clinical significance (as assessed by the Investigator) will be reported.

4.1.6 Physical Examination

Full and symptoms-directed physical examinations will be performed in accordance with the Schedule of Study Events (Section 2.5).

The following body systems will be assessed ('Normal' or 'Abnormal') and findings and clinical significance (as assessed by the Investigator) will be reported on the Physical Examination eCRF page:

- Head, eyes, ears, nose, and throat.
- Cardiovascular system
- Dermatological system
- Musculoskeletal system
- Respiratory system
- Gastrointestinal system
- Neurological system
- Other abnormalities.

4.1.7 Fasting Status and Water Restrictions

The dates and time of the meals before and after the study drug administrations will be collected on the 'Overnight Fasting Status' and 'Post-Dose Fasting Status' CRF pages. Water intake will be restricted before and after the study drug administration and the timing of the restriction period will be reported on the 'Water Restriction' CRF pages.

4.2 Pharmacokinetic Concentrations

Plasma PK samples will be collected during Treatment Period 1 and Period 2 at the time points specified in the Schedule of Study Events (Section 2.5). The actual sample collection dates and times will be reported on the 'PK Blood Collection' CRF pages.

The actual elapsed time (hours) from the reference study drug administration in each period will be calculated as the difference between the date/time of the sample collection at the nominal time point and the date/time of the study drug administration for the specific period.

The time deviation at each time point (hours), defined as the difference between the nominal (planned) and actual collection times will be calculated as the difference between the nominal collection time point value (i.e., 2 hours post-dose will be 2 hours) and the elapsed time based on the actual collection date and time.

Deviations from the collection time points will be used to identify out of window samples that may be excluded from the PK analysis if deemed to have a major impact on the overall analysis.

Plasma concentrations of sitravatinib will be determined using a validated analytical procedure. Specifics about the analytical method will be provided in the bioanalysis report. Concentrations data will be provided electronically by the analysing laboratory.

The Lower Limit of Quantitation (LLOQ) for sitravatinib is 0.05 ng/mL.

Concentrations below the LLOQ (BLQ) observed prior to the maximum observed concentration (C_{max}) for the specific period will be set to zero for all calculations and analyses. BLQ concentrations observed after C_{max} will be treated as missing.

4.3 Pharmacokinetic Parameters

The PK parameters described in this section will be derived based on the plasma sitravatinib concentration-time profiles as observed after the study drug administrations on Day 1 of each treatment period. The parameters will be calculated separately for each treatment period based on concentrations collected during the specific period.

BLQ concentrations observed prior to the maximum observed concentration (C_{max}) for the specific period will be set to zero and BLQ concentrations observed after C_{max} will be treated as missing in all

Sponsor: BeiGene, Ltd.
Protocol Number: BGB-Sitravatinib-101

parameter calculations. Derivations will be based on the actual elapsed time (hours) since the study drug administration in the specific period.

The pharmacokinetic concentrations will be processed using standard noncompartmental analytical procedures to derive the required parameters. The software used for the analysis will be Phoenix™ WinNonlin® v8.2 (Pharsight Corporation, USA).

The PK parameters described in Table 4 will be derived for each period provided that the required concentrations data are available. Supporting PK parameters (used to derive or assess the validity of $t_{1/2}$ and associated parameters) which include R^2 , number of points for estimation of k_{el} and $\%AUC_{ext}$ will only be listed and not included in the summary tables.

Table 4 Plasma PK Parameters

PK Parameter (Unit)	Method
C_{max} (ng/mL)	Maximum observed plasma concentration.
t_{max} (h)	Time to reach maximum plasma concentration.
AUC_{0-t} (h*ng/mL)	Area under the plasma concentration-time curve from the time of the dose administration to the time of the last measurable concentration calculated by the linear up log down trapezoidal method.
$t_{1/2}$ (h)	Elimination half-life associated with the terminal slope (k_{el}) of the semilogarithmic drug concentration-time curve, calculated as $0.693/k_{el}$.
AUC_{0-inf} (h*ng/mL)	Area under the plasma concentration-time curve from the time of the dose administration to time infinity calculated by the linear up log down trapezoidal method.
CL/F (L/h)	The apparent total clearance.
V_z/F (L)	The apparent total volume of distribution.
R^2 (%)	R-squared.
No. of Points (%)	No. points for determination of k_{el} .
k_{el} (1/h) (%)	Apparent terminal elimination rate constant.
$\%AUC_{ext}$ (%) (%)	Percentage of the area under the plasma concentration-time curve extrapolated from the time of the last measurable concentration to time infinity as a percentage of AUC_{0-t}
DN C_{max} (ng/mL)/mg	Dose-normalized C_{max} will be calculated by dividing C_{max} by the administered dose.
DN AUC_{0-t} (h*ng/mL)/mg	Dose-normalized AUC_{0-t} will be calculated by dividing AUC_{0-t} by the administered dose.
DN AUC_{0-inf} (h*ng/mL)/mg	Dose-normalized AUC_{0-inf} will be calculated by dividing AUC_{inf} by the administered dose.
F_{rel} (%)	Relative bioavailability (F_{rel}) (%) will be calculated based on the AUC_{0-inf} results using the following formula: $F_{rel} (\%) = 100 * ([AUC_{MSC} * 120 \text{ {the FCB dose}}] / [AUC_{FBC} * 100 \text{ {the MSC dose}}])$

(%) Derived to determine $t_{1/2}$, results will only be listed.

Results for $t_{1/2}$, AUC_{0-inf} , CL/F and V_z/F will only be included in the summary statistics if the following criteria are met:

- A minimum of 3 measurable concentrations-time points is available during log-linear portion of the terminal elimination phase (excluding C_{max}), i.e., No. of Points is ≥ 3 .
- $R^2 > 0.80$.
- $\%AUC_{ext} < 20\%$.

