8.3. Pharmacokinetic Analyses

The plasma PK parameters of sitratavinib will be calculated using standard noncompartmental methods, based on actual sample collection time rather than scheduled times.

For the analysis of relative bioavailability between sitratavinib malate salt (test) and sitratavinib free base (reference), log-transformed PK parameters ($AUC_{0-\infty}$, AUC_{0-t} , and C_{\max}) for sitratavinib will be analyzed by a mixed effect model. This model will include formulation, period, and sequence as fixed effects and subject as a random effect.

For PK parameters ($AUC_{0-\infty}$, AUC_{0-t} , and C_{\max}) for sitratavinib, a point estimate and its associated 90% CI will be constructed for the difference between test and reference capsules and this difference and its 90% CI will be exponentiated to obtain the estimate of the ratio of geometric least-squares means and its 90% CI. The ratio of test formulation to reference formulation will be calculated on both non-dose-normalized and dose-normalized PK parameters. Estimated geometric means will also be presented by each formulation.

All other PK parameters will not be subject to inferential statistical analysis and only descriptive statistics (n, arithmetic mean, standard deviation, arithmetic CV, geometric mean, geometric CV, median, min, max, as appropriate) will be presented for them.

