3.3 Pharmacokinetic (PK) Parameters Analysis Set

The PK Parameters Analysis Set is defined as all subjects who received at least one dose of sitravatinib and have at least one PK parameter of sitravatinib.

The following are reasons for exclusion from the PK Parameters Analysis Set:

- Subject did not receive at least one dose of sitravatinib.
- Subject does not have at least one sitravatinib PK parameter.
- Subject experienced an event that may affect their PK profile (e.g., has an AE of vomiting that occurs at or before 2 times median T_{max}).

At the discretion of the pharmacokineticist, PK parameter results may also be excluded from the analysis if it is not sufficient to characterize the PK profile (e.g. percentage of AUC extrapolation >20%).

The PK Parameters Analysis Set will be used as the analysis set for the PK parameter outputs.

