5.1.3 Default Descriptive Statistics and Data Presentation Rules

Unless otherwise stated, summary statistics including the number of subjects, mean, standard deviation, median, minimum, and maximum, will be presented for all continuous variables. Minimum and maximum values will be presented to the same decimal precision as the raw values, the mean and median values to one more, and the standard deviation, to two more decimal places than the raw values. Derived values will be presented to 4 significant digits.

For categorical variables, per category, the absolute counts (n) and percentages (%) of subjects with data, and if appropriate, the number of subjects with missing data, will be presented. Unless specifically stated otherwise, denominator for all percentage calculations will be the number of subjects in the specific treatment sequence/group and analysis population. All percentages will be presented to one decimal place.

For PK concentration and parameters data, descriptive statistics will include the number of non-missing values (n), the arithmetic mean, standard deviation (SD), median, minimum, maximum, coefficient of variation (CV), geometric mean, geometric SD and geometric CV values, as appropriate. For the PK concentration summaries, the number of concentrations below the limit of quantification will also be presented.

The minimum and maximum values will be displayed to the same decimal precision as the source data, the arithmetic mean and median values will be displayed to one more decimal, and the SD values will be displayed to two more decimals than the source data for the specific variable. The geometric mean values will be presented to one more decimal place than the arithmetic mean and the CV and geometric CV values will be converted to percentages and presented to one decimal place.

If required, results will be rounded using the SAS® function ROUND. Values will be rounded after all calculations have been performed.

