6.9.2 Pharmacokinetic Parameters

The calculated plasma PK parameters described in Section 4.3 will be summarised by treatment group using the statistics described in Section 5.1.3. The summary tables will be based on the PK Parameters Analysis Set.

Relative bioavailability will be summarised separately based on the Relative Bioavailability Analysis Set.

The analysis of the relative bioavailability between the two different formulations of sitravatinib (sitravatinib MSC as test and sitravatinib FBC as reference) will be based on the dose-dependent parameters AUC_{0-inf} , AUC_{0-t} and C_{max} . The \log_e -transformed parameters will be analyzed separately using a mixed effect model (data permitting) with the treatment group (formulation), sequence and period as fixed effects and subject nested within sequence as a random effect. The geometric means (exponentiated least squares means) and the associated 90% confidence intervals for each treatment group and the geometric mean ratio (exponentiated difference between sitravatinib MSC least-squares mean as test and sitravatinib FBC least-squares mean as reference) and the associated 90% confidence interval will be presented. The geometric mean ratios and the associated confidence

Sponsor: BeiGene, Ltd.

Protocol Number: BGB-Sitravatinib-101

intervals will be expressed as percentages. Bioequivalence will be concluded if the 90% confidence intervals of the geometric mean ratios of all three parameters lies entirely within the bioequivalence interval of 80% to 125%. Refer to Appendix 3 for the SAS® code that will be used for the analysis. The analysis will be based on the Relative Bioavailability Analysis Set.

The analysis will also be repeated based on the dose-normalized AUC_{0-inf} , AUC_{0-t} and C_{max} results.

The parameters AUC_{0-inf} , AUC_{0-t} and C_{max} will also be presented graphically by means of box-and-whiskers plots. The results for the two treatment groups will be presented on the same plot. The dose-normalized AUC_{0-inf} , AUC_{0-t} and C_{max} results will also be plotted separately. The plots will be based on the Relative Bioavailability Analysis Set.

All parameter results will be listed based on the PK Parameters Analysis Set, and any results that may have been excluded from the summary tables will be flagged. The SAS® outputs generated by the respective models will be presented in listings.

7. Changes to the Planned Analyses

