Attachment 1 List of Tables, Listings and Figures

Tables
Table 14.1.1.1 Analysis Sets (Safety Analysis Set)
Table 14.1.1.2 Subject Disposition (Safety Analysis Set)
Table 14.1.2.1 Protocol Deviations (Safety Analysis Set)
Table 14.1.3.1 Demography (Safety Analysis Set)
Table 14.1.4.1 Baseline Subject Characteristics (Safety Analysis Set)
Table 14.1.5.1 Medical History (Safety Analysis Set)
Table 14.2.1 Plasma Sitratatinib Pharmacokinetic Concentrations (Pharmacokinetic Concentrations Analysis Set)
Table 14.2.2 Plasma Sitratatinib Pharmacokinetic Parameters (Pharmacokinetic Parameters Analysis Set)
Table 14.2.3 Dose-Normalized Plasma Sitratatin b Pharmacokinetic Parameters (Pharmacokinetic Parameters Analysis Set)
Table 14.2.4 Relative Bioavailability (Relative Bioavailability Analysis Set)
Table 14.2.5 Analysis of Bioavailability (Relative Bioavailability Analysis Set)
Table 14.3.1 Concomitant Medications by Preferred Name (Safety Analysis Set)
Table 14.3.2.1 Overall Summary of Adverse Events (Safety Analysis Set)
Table 14.3.2.2 Treatment-Emergent Adverse Events by System Organ Class and Preferred Term (Safety Analysis Set)
Table 14.3.2.3 Serious Treatment-Emergent Adverse Events by System Organ Class and Preferred Term (Safety Analysis Set)
Table 14.3.2.4 Treatment-Related Treatment-Emergent Adverse Events by System Organ Class and Preferred Term (Safety Analysis Set)
Table 14.3.2.5 Treatment-Emergent Adverse Events Leading to Study Drug Withdrawal by System Organ Class and Preferred Term (Safety Analysis Set)
Table 14.3.2.6 Treatment-Emergent Adverse Events Leading to Study Withdrawal by System Organ Class and Preferred Term (Safety Analysis Set)
Table 14.3.2.7 Treatment-Emergent Adverse Events by System Organ Class, Preferred Term and Severity Rating (Safety Analysis Set)
Table 14.3.2.8 Treatment-Emergent Adverse Events by System Organ Class, Preferred Term and Relationship to Study Drug (Safety Analysis Set)
Table 14.3.3.1 Summary of Hematology Results (Safety Analysis Set)
Table 14.3.3.2 Summary of Biochemistry Results (Safety Analysis Set)
Table 14.3.3.3 Summary of Urinalysis Result Classifications (Safety Analysis Set)
Table 14.3.4.1 Summary of ECG Results (Safety Analysis Set)
Table 14.3.4.2 Summary of ECG Overall Assessments (Safety Analysis Set)
Table 14.3.5 Summary of Vital Signs Results (Safety Analysis Set)
Listings
Listing 16.2.1.1 Analysis Sets (Safety Analysis Set)
Listing 16.2.1.2 Subject Disposition (Safety Analysis Set)

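### SAP Table 4 expresses %AUCext relative to AUC0-t instead of AUC0-inf, so the 20% rule for the descriptive PK summaries cuts at 16.7% of AUC0-inf and the listings overstate extrapolation

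*SAP*

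**What the plan says.** SAP Section 4.3, Table 4, gives %AUCext as the area from the last measurable concentration "to time infinity as a percentage of AUC_{0-t". Below the table, the results for t1/2, AUC0-inf, CL/F and Vz/F "will only be included in the summary statistics if the following criteria are met": at least three points in the terminal phase, R² above 0.80, and %AUCext below 20%. %AUCext itself is a supporting parameter; these "will only be listed and not included in the summary tables".

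SAP Section 3.3 has a separate, discretionary exclusion, with "percentage of AUC extrapolation >20"% as its example. It names no denominator and does not refer to Table 4.

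The summaries concerned are those of SAP Attachment 1, "Table 14.2.2 Plasma Sitratatinib Pharmacokinetic Parameters", with the statistics of SAP Section 5.1.3, including "coefficient of variation (CV), geometric mean, geometric SD and geometric CV values". Protocol Section 8.3 says of everything other than AUC0-inf, AUC0-t and Cmax: "All other PK parameters will not be subject to inferential statistical analysis and only descriptive statistics". SAP Section 6.9.2 keeps all results in the listings, where "any results that may have been excluded from the summary tables will be flagged".

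Neither document defines %AUCext on AUC0-inf anywhere.

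**The concern.** AUC0-t leaves out the extrapolated area, so the quantity in Table 4 is the ratio of unobserved to observed area. It is not the share of the total that was extrapolated, and it has no ceiling at 100%. A reader of a 20% extrapolation limit would take it as 20% of AUC0-inf.

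The definition matters because a mandatory rule rests on it. Profiles whose true share lies between 16.7% and 20% leave the summaries of t1/2, AUC0-inf, CL/F and Vz/F because of the denominator alone. At a fixed last sampling time these are profiles with long half-lives, so the t1/2 summary is pulled down. For t1/2, CL/F and Vz/F, descriptive statistics are the only summary analysis planned. The listed %AUCext, which is there so that a reader can judge the terminal phase, is also overstated.

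**Working it through.** The 20% is a preset limit, so there is no plan figure to reproduce. The check converts it to the AUC0-inf scale and then asks which profiles change status.

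**Inputs from the documents**
- Denominator AUC0-t and limit below 20%: SAP Section 4.3.
- Sampling at 0, 0.5, 1, 2, 4, 6, 8, 12, 24, 48, 72 and 168 h, with a ±2 h window at 168 h: Protocol Appendix 6.
- Linear-up log-down trapezoidal rule: SAP Table 4.
- Median half-life 42 to 58 h and median Tmax about 3 to 8 h, both in patients in Study 516-001: Protocol Section 1.3.2.

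**Assumed, not in the documents**
- Mono-exponential decline, or a one-compartment oral profile for the check on the sampling grid.
- For the illustration only: log-normal half-life with a between-subject CV of 20% to 40%, and 24 profiles per formulation.

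**Step 1: conversion.** Let E be the extrapolated area, so AUC0-inf = AUC0-t + E. If x = E/AUC0-t, the share of the total is x/(1 + x). At x = 0.20 this is 0.20/1.20 = 16.7%. In reverse, a true share f prints as f/(1 − f): 0.20/0.80 = 25%, and 0.30/0.70 = 42.9%.

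**Step 2: half-life cut-offs.** With the last quantifiable sample at T, f = 2^(−T/t1/2), so a limit f corresponds to t1/2 = T/log2(1/f).

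| Last quantifiable sample | As written (f = 1/6) | AUC0-inf scale (f = 1/5) |
|---|---|---|
| 168 h | 168/log2(6) = 65.0 h | 168/log2(5) = 72.4 h |
| 166 to 170 h (window) | 64.2 to 65.8 h | 71.5 to 73.2 h |
| 72 h | 27.9 h | 31.0 h |

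Running the noncompartmental calculation on the planned sampling grid, with the terminal slope from 48, 72 and 168 h, gives almost the same cut-offs: 64.7 and 72.1 h for Tmax 3 h, 64.5 and 71.9 h for Tmax 5 h, 64.2 and 71.5 h for Tmax 8 h.

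**Step 3: profiles at the documented medians.**
- T = 168 h: 2^(−168/42) = 6.25% and 2^(−168/58) = 13.4% of AUC0-inf, which print as 6.7% and 15.5%. Both pass either way.
- T = 72 h: 30.5% and 42.3%. Both fail either way.

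So only profiles followed to 168 h with half-lives of about 65 to 72 h change status, apart from a band of 27.9 to 31.0 h when T is 72 h, which lies below the documented medians.

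**Step 4: illustration under the assumed CV.** Let m = ln(median), σ = √ln(1 + CV²) and a = (ln(cut-off) − m)/σ. The share of profiles between the two cut-offs is the difference of Φ(a). The geometric mean of the profiles that remain is exp(m − σφ(a)/Φ(a)). T = 168 h throughout.

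| Median t1/2 | Share between cut-offs, CV 20/30/40% | Change in summarised geometric mean, as written against AUC0-inf scale |
|---|---|---|
| 42 h | 1.1 / 3.7 / 5.0% | −0.5 / −2.0 / −3.1% |
| 50 h | 6.2 / 8.2 / 7.9% | −2.2 / −3.7 / −4.4% |
| 58 h | 15.1 / 12.3 / 10.1% | −4.4 / −5.2 / −5.5% |

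Multiplied by 24, the shares are 0.3 to 3.6 profiles per formulation. At 50 h and CV 30%, σ = 0.294 and a = 0.893 and 1.259. About 2.0 of 24 profiles fall between the cut-offs, and the summarised geometric mean is 45.4 h as written against 47.1 h on the AUC0-inf scale. Without any filter it would be 50.0 h, so the 20% rule itself removes 2.9 h and the denominator a further 1.7 h.

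**The case against.** The case for leaving the text alone has several parts.

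- *Table 4 is executable and the limit is applied to the quantity it defines; no stated figure fails to reproduce.* This is true, so the fault lies in the definition and not in a miscalculated number. It still stands, because an extrapolated percentage not taken of the total does not measure the extrapolated share, and the SAP neither states nor justifies an effective 16.7% limit.
- *The error makes the rule stricter, so no poorly characterised profile gets in.* True. The cost is the loss of profiles with a true share between 16.7% and 20%.
- *Profiles at the documented medians do not change status, and the practical effect rests on an assumed CV applied to medians from patients.* True. Step 4 shows only what is plausible. Steps 1 and 2 need no CV, and 65.0 h is only 12% above the upper median (65.0/58 = 1.12).
- *Most of the downward pull on t1/2 comes from the 20% rule itself.* True in the worked case: 2.9 h against 1.7 h. Only the second part is attributed to the denominator here.
- *Excluded results stay listed with a flag, and a reader can recompute the share from the two listed AUCs. No conclusion on relative bioavailability is shown to change.* This stands and limits the scope. The criteria are written for the summary statistics and are not stated to govern the mixed model.

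The documents also do not show what will be programmed. If the program already uses AUC0-inf, Table 4 misdescribes the output and needs the same correction.

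**Conclusion.** The definition is wrong as written and should be corrected. The 20% criterion for summarising t1/2, AUC0-inf, CL/F and Vz/F acts at 16.7% of AUC0-inf, and every listed %AUCext is too high by the factor AUC0-inf/AUC0-t. These two results are algebra and need no assumption.

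The half-life band affected, about 65.0 to 72.4 h, assumes a last quantifiable sample at 168 h and mono-exponential decline; the check on the sampling grid moves its limits by less than 1 h. The illustrative size, 0.3 to 3.6 of 24 profiles and −0.5% to −5.5% on the t1/2 geometric mean, rests on an assumed CV of 20% to 40% and on medians from patients, and should carry little weight.

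For t1/2 the direction is downward. For the AUC0-inf summary it is not established. Cmax and AUC0-t are untouched by these criteria, and no effect on the test/reference ratio is claimed.

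**What to change.** In SAP Table 4, define %AUCext = 100 × (AUC0-inf − AUC0-t)/AUC0-inf. Keep the 20% criterion in Section 4.3 on that definition, and add a cross-reference in Section 3.3 so that its 20% example uses the same quantity. If AUC0-t is really intended as the denominator, the SAP should say so and justify an effective limit of 16.7% of AUC0-inf.

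The cost is one denominator and one cross-reference, with no extra data or resources.
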